5.1. Objectives

5.1.1. Primary Objective(s)

The primary objective of the study is to demonstrate the accuracy of Enlite sensor when connected to iPro2 when used over a period of six days.

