5.2.6. Subject Feedback

Descriptive summary will be used to characterize study questionnaire results. The questionnaire will use a Likert scale rating to assess their Enlite Sensor experience.

6. Study Design

This study is a multi-center, randomized, prospective single-sample correlational design without controls. Up to 72 subjects will be enrolled in order to have approximately 60 subjects complete the study. Three investigational centers in China will be used during this study.

Each subject will wear the following devices:

- Two Enlite Sensors, each connected to an iPro2, for approximately 6 days

Sensor Location:

- The 2 Enlite Sensors be worn in the abdomen area. Investigational center staff will insert sensors and connect to the iPro2s.

During the study, each subject will be randomized and undergo one YSI FST (Day 1, 3-4, or 6).

On the evening prior to FST, subjects will be asked to fast for approximately 12 hours and adjust their insulin and medications according to routine care (for example as they would do for fasting lipid panel). Subjects may fast for shorter period of time **based on investigator discretion**.

The subject should be in fasting status upon arrival hospital to start FST process. **The feeding protocol may be modified based on investigator discretion.**

The duration of FST will be approximately 7 hours.

During the study, subjects will continue with their current diabetes regimen independent of the study devices. Subjects will be instructed by the investigational center that they are not to use the study devices (except for the study meter) for the management of their diabetes. The Study Meter may be used for treatment decisions and calibration of Enlite Sensor.

Fingerstick Testing: A minimum of 4 fingerstick glucose readings per day will be requested for subjects. Subjects should test prior to meals and at bedtime.

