9.1. Study Timeline

The subject's participation from study start to completion is approximately 1 – 3 weeks (including replacement sensor wear and repeat in clinic procedures).

Additional rescheduled visits could occur if Enlite Sensors dislodge and new Enlite Sensors must be re-inserted (See Replacement Sensors, Section 9.6)

- Visit 1: Consent and Screening
- Visit 2: Randomization
 - Visit 1 and 2 can be combined however all eligibility criteria on Visit 1 should be met including review of Hct prior to Visit 2.
 - Visit 1 and Visit 2 should be no more than 2 weeks apart.
- Visit 3: Study Training and iPro2 Placement & Sensors Insertion
 - Two Enlite Sensors, each connected to an iPro2
 - Dispense Patient Log Sheet
- Visit 4: YSI FST
 - Study training and iPro2 placement & sensors insertion (Day 1 subjects who have not already received study training and iPro2 placement and sensor insertion from Visit 3)
 - Subjects will undergo one YSI FST on any one of the following sensor wear days:
 - Day 1 (1 – 25 hours)
 - Day 3 – 4 (49 – 97 hours)
 - Day 6 (121 – 145 hours)
- Visit 5: End of Study (EOS) Visit
 - iPro2 removed (**Please note that the subject should target wearing the device for 145 hours or longer from time of insertion**)
 - Investigational center staff will:
 - Download the iPro2 data from CareLink iPro following completion of the study devices wear
 - Obtain subject's Study Meter BG values and enter into CareLink iPro
 - Collect subject's Patient Log Sheet
 - Provide iPro2 data to sponsor
 - Return study devices
 - Subject complete questionnaires
 - Random assignment for primary sensor and secondary sensor via RDC

Guidelines for Combining Visits:

- All subjects meeting eligibility criteria:

[figure not shown]
- Visit 1 and 2 can be combined, however all eligibility criteria on Visit 1 should be met, including review of Hct prior to Visit 2.
- Subjects randomized to FST Day 1
 - Subjects doing FST on Day 1 may combine Visit 2 and Visit 3 as long as they are able to perform Visit 4 FST in the second half of FST day.
 - For example, subject does Visit 1 and 2 in the morning and performs Visit 3 in the afternoon. Subject comes in the next day for Visit 4 in the morning within approximately 25 hours from time of insertion.
- Subjects randomized to FST Day 3-4
 - May combine Visit 2 and Visit 3
- Subjects randomized to FST Day 6
 - May combine Visit 2 and Visit 3
 - May combine Visit 4 and Visit 5 as long as the subject has worn N=145 hours.

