9.2.3.1. Procedures Including YSI FST Timing and Fingerstick Requirements

Table 2. YSI FST Timing and Fingerstick Requirements

Visit	Sensor Wear	Group	Timing of YSI FST from Sensor Insertion T=0	Timing of fingerstick from Sensor insertion T=0
4	Day 1	Day 1	The 7 hour FST may be performed anytime between Time = 1 hour to Time = 25 hours	
 Time = 0 hour 
Enlite Sensor insertions will be performed at the investigational center.
 
The 0 hour represents the time after sensors have been connected to the iPro2 .
 
 Target Time = 60 minutes check SMBG and record in Patient Log Sheet Target Time =3 hours and check SMBG and record in Patient Log Sheet 
Minimum of 4 fingerstick glucose readings per day and record in Patient Log Sheet

4	Day 3-4	Day 3-4	The 7 hour FST may be performed anytime between Time = 49 hours to Time = 97 hours	
Minimum of 4 fingerstick glucose readings per day and record in Patient Log Sheet

CIP313 Clinical Investigation Plan

10688326DOC

Version B

Page 37 of 87

Visit	Sensor Wear	Group	Timing of YSI FST from Sensor Insertion T=0	Timing of fingerstick from Sensor insertion T=0
4	Day 6	Day 6	The 7 hour FST may be performed anytime between Time = 121 hours to Time = 145 hours	Minimum of 4 fingerstick glucose readings per day and record in Patient Log Sheet

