14.12.6. Home-Use Portion Data Analysis

Data from the home-use portion will be described. Analysis will include but not be limited to: 20% mean agreement rate (± 20 mg/dL (1.1 mmol/L) when Reference BG less than or equal to (\leq) 80 mg/dL (4.4 mmol/L)) for all fingersticks (capillary SMBG) collected, Clarke Error Grid, other accuracy analysis, ARE, bias, correlation between Enlite Sensor and SMBG and Bland-Altman plots. In addition, 20% mean agreement rate (± 20 mg/dL (1.1 mmol/L) when Reference BG less than or equal to (\leq) 80 mg/dL (4.4 mmol/L)) will be described by subgroups of YSI FST. The number of actual calibrations performed per day by study subjects will be tabulated and presented:

- **FST:**
 - Day 1
 - Day 3-4

- Day 6

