7.9 Other Descriptive Endpoints

- Data from the home-use portion will be described. Analysis will include but not be limited to: 20% mean agreement rate (± 20 mg/dL (1.1 mmol/L) when Reference BG less than or equal to (\leq) 80 mg/dL (4.4 mmol/L)) for all fingersticks (capillary SMBG) collected, Clarke Error Grid Analysis (EGA), Consensus Error Grid analysis, Absolute Relative Difference (ARD), bias, correlation between Enlite Sensor and fingersticks (capillary SMBG), and Bland-Altman plots. In addition, 20% mean agreement rate (± 20 mg/dL (1.1 mmol/L) when Reference BG less than or equal to (\leq) 80 mg/dL (4.4 mmol/L)) will be described by the subgroups mentioned below: frequent sampling. The number of actual calibrations performed per day by study subjects will be tabulated and presented.
- Similar descriptive subgroup analysis of Enlite Sensor performance with YSI in all devices will be performed.
 - **FST:**
 - Day 1
 - Day 3-4
 - Day 6
- Precision analysis: ARD, bias, and 20% mean agreement rate (± 20 mg/dL (1.1 mmol/L) when Reference BG less than or equal to (\leq) 80 mg/dL (4.4 mmol/L)) will be performed.

This part of indicators will be summarized by descriptive statistics. The analysis method will be referred to section 7.2.

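### Home-use agreement is broken down only by FST subgroup, which does not track sensor age and gives wear Days 2 and 5 no result of their own

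*Protocol*

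**What the plan says.** - **Objective.** Protocol 5.1.1 sets out to "demonstrate the accuracy of Enlite sensor when connected to iPro2 when used over a period of six days".
- **YSI sessions.** Each subject has one 7-hour FST, on the day to which he or she was randomised. Protocol 9.1 and Table 2 give three windows from insertion: 1-25 h, 49-97 h and 121-145 h. For the middle group, for example, "The 7 hour FST may be performed anytime between Time = 49 hours to Time = 97 hours".
- **FST group.** Protocol 9.4 makes it a randomised assignment that the subject keeps throughout the study.
- **Fingersticks.** Protocol section 6: "A minimum of 4 fingerstick glucose readings per day will be requested for subjects". This applies whatever the FST group.
- **Home-use analysis.** Protocol 14.12.6 gives the agreement rate "for all fingersticks (capillary SMBG) collected, Clarke Error Grid, other accuracy analysis" and further pooled measures. It then says that the agreement rate "will be described by subgroups of YSI FST" and lists Day 1, Day 3-4 and Day 6. SAP 7.9 has the parallel wording: the rate "will be described by the subgroups mentioned below: frequent sampling". SAP 7.13, which lists changes to the planned analysis, leaves this as it is.
- **YSI analysis by day.** Protocol 14.12.5 and SAP 7.9.5 give absolute relative difference, bias and Bland-Altman plots by day, and agreement by FST day, for the three FST periods.

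**The concern.** A six-day accuracy claim invites the question of whether accuracy changes as the sensor ages. The YSI data answer it at three periods only, and each period is measured in different subjects. The fingersticks are the only reference readings that follow the same subject through the whole wear, and the only ones of any kind on Days 2 and 5.

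The plan splits these readings by a label that fixes when the clinic session happens, not when a home fingerstick is taken. The three rows could look alike whether or not the sensor drifts, and a reader could take that as evidence of stability. The wording can also be read as the wear day of the fingerstick, so two programmers could produce two different tables from the same sentence.

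**Working it through.** The plan gives no figure of its own on this point. Its sample size was checked as background. A one-sample t-test at one-sided 0.025, with difference 0.72 - 0.60 = 0.12 and SD 0.32, needs 58 subjects (power 80.2%), as stated. Nothing below changes it.

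**1. YSI coverage** (windows from Protocol 9.1 and Table 2)

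- Covered: (25 - 1) + (97 - 49) + (145 - 121) = 24 + 48 + 24 = 96 h.
- Span: 145 - 1 = 144 h. Not covered: 144 - 96 = 48 h, or 33%.
- The gaps are 25-49 h (Day 2) and 97-121 h (Day 5).

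**2. Fingersticks available** (minimum 4 per day, 6 days, about 60 completers)

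- Total: 4 x 6 x 60 = 1,440. Per wear day: 4 x 60 = 240. Days 2 and 5 together: 480.
- Per FST group: 4 x 6 x 20 = 480. This assumes equal allocation, which the documents do not state.

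**3. Reading A: rows are randomised groups.** Take an assumed agreement profile over Days 1 to 6 of 60, 70, 80, 80, 75 and 65%, common to all groups.

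- Each group averages over all six days: (60 + 70 + 80 + 80 + 75 + 65)/6 = 71.7%.
- A simulation of 2,000 trials (60 subjects, 4 pairs per day, between-subject SD 10 points) gave 71.7, 71.6 and 71.6% by FST group, and 60.0, 70.0, 79.9, 79.9, 74.8 and 65.1% by wear day. A 20-point range over time disappears in the first table and is recovered in the second.
- The standard error per wear day was 2.8 to 3.3 points. By formula at 70%: the between-subject variance is 0.01, the within-subject variance is (0.70 x 0.30 - 0.01)/4 = 0.05, and the square root of 0.06/60 is 0.032.

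The profile is illustrative. Any common profile gives equal expected rows if each group has the same mix of days. That mix is only approximately equal. Table 2 lists fingersticks at 60 minutes and 3 hours in the Day 1 row only. If these are additional to the four, the Day 1 group expects (6 x 60 + 4 x (70 + 80 + 80 + 75 + 65))/26 = 1,840/26 = 70.8%, a shift of 0.9 points against the 20-point range.

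**4. Reading B: rows are the wear day of the fingerstick.** The rows hold (1 + 2 + 1) x 240 = 960 of the 1,440 fingersticks. The other 480, from Days 2 and 5, have no row.

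Under either reading, no specified home-use result is separate for Day 2 or Day 5.

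**The case against.** Several points on the other side stand.

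- **A reader might infer that Days 2 and 5 are never assessed.** The documents do not support that. All fingersticks enter the pooled home-use summary and the difference tables against the meter (Protocol 14.12.1, SAP 7.9.1). These days are assessed, but not shown separately.
- **A reader might infer that the plan says nothing about accuracy over time.** It does, through the YSI results by FST day. Sampling three periods is a legitimate design choice, and the objective does not promise an estimate for each day. What remains is that these are between-subject comparisons at three periods.
- **A reader might infer an expected contrast of exactly zero between FST groups.** That is not established. Besides the early Day 1 fingersticks, Protocol 9.6 provides for re-insertion only when a sensor dislodges before the FST or within its first 5 hours, so the mix of sensor ages can differ by group. This does not make FST group a usable measure of sensor age.
- **The fingersticks are not an independent reference.** CareLink iPro merges sensor and meter data to produce the sensor values (Protocol 7.2.4), and the Study Meter calibrates them (Protocol 9.10). A home-use pair may compare a sensor value with one of its own calibration inputs, which can mask drift. This is the strongest objection: a wear-day table cannot replace YSI data on Days 2 and 5.
- **The list is open-ended.** "Analysis will include but not be limited to" permits a wear-day table, and the SAP's table shells are in an appendix that is not among the documents. But permission is not prespecification, and neither text asks for such a table.
- **The analysis is descriptive.** Pass/fail rests on the YSI primary endpoint alone (Protocol 14.9).

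**Conclusion.** The concern holds as a cheap improvement to a descriptive table. The one breakdown specified for home-use agreement either does not index sensor age or, on the other reading, omits two of the six wear days. Those are the same days that have no YSI reference: 48 of 144 hours, and about 480 of 1,440 fingersticks at the protocol minimum with 60 completers. The loss of the time pattern under the group reading rests on a profile common to the randomised groups and a roughly equal spread of fingersticks over days. Small departures from that are expected and do not alter the conclusion.

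A reader might go further and conclude that the six-day objective fails or that the primary result is compromised. The documents do not support that: the primary test, the sample size of 58 and the 60% criterion do not use these data.

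**What to change.** In Protocol 14.12.6 and SAP 7.9, replace the FST-subgroup split of home-use agreement with a table by wear day of each fingerstick:

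- **Bins**, in hours from insertion, aligned to the protocol windows: 1-25, 25-49, 49-73, 73-97, 97-121 and 121-145. State which bin a boundary time belongs to, and apply the 144-hour functional-life cut of SAP 6.6.4.
- **Summary:** the agreement rate per subject within each bin, then the mean over subjects, with the numbers of subjects and pairs.
- **Label:** descriptive, meter-referenced, and not independent of the sensor values because the same Study Meter readings calibrate the sensor.
- **Report:** state that YSI-based accuracy covers Days 1, 3-4 and 6 only, and that Days 2 and 5 rest on fingersticks.

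The cost is a wording change and one re-cut table. Insertion time is documented at Visit 3, the meter clock is synchronised to the study clock, and pairing within 5 minutes already needs the fingerstick times. The main downside is that agreement with a calibrating meter can hide drift, so the Day 2 and Day 5 figures could reassure more than they should; the label is there to prevent that.

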14.13. Safety

For Safety analysis, no formal hypothesis testing will be performed. Descriptive analytics will be used to summarize safety events. Safety events which will be characterized include:

- Skin assessment of Enlite Sensor insertion sites
- All AEs to include but not limited to:
 - Device Related AE
 - Procedure Related AE
 - SAE
 - SADE
 - UADE
 - Severe Hypoglycemia
 - DKA

14.14. Device Deficiencies

Descriptive summary will be used to characterize device deficiencies

14.15. Subject Feedback

Descriptive summary will be used to characterize study questionnaire results. The questionnaire will use a Likert scale rating to assess their Enlite Sensor experience.

14.16. Clinical Study Report

The Clinical Study Report will be compliant with CFDA 2016 No. 58 Announcement Annex 5 "Template of Clinical Trial Report of Medical Devices". Any deviations from original statistical plan and the rationale will be described in the Clinical Study Report.

There will be no interim analysis perform during the study so therefore there are no criteria and/ reasons for trial termination based on statistics.

15. Ethics

15.1. Statement(s) of Compliance

This study is a pre-market clinical trial for product registration. The study will be conducted in accordance with the laws and regulations of China, including any future applicable laws and regulations in China.

This protocol, any subsequent amendments to this protocol, the Informed Consent/Assent form, subject material and any form of subject recruitment information (e.g. advertisements) relating to this study will be approved by the responsible EC in accordance with CFDA Order No. 25 and local regulatory requirements as applicable. The study will not start until EC approval has been granted, the Sponsor has cleared the investigational center to begin the study, and the investigational center staff has been appropriately trained to conduct the study. Copies of all relevant correspondence between the investigational center and the EC will be retained at investigational center with copies forwarded to the Sponsor for their files.

Regulatory Compliance

To protect the rights and welfare of patients, this clinical study will be conducted in compliance with the latest version of the Declaration of Helsinki, the Clinical Trial Agreement and CIP, the laws and regulations of China including Good Clinical Practice for Medical Devices (CFDA Order No. 25), Announcement of CFDA on Filing of Medical Device Clinical Trial (2015, No.87) and also including applicable data protection laws. Investigational centers will also comply with any additional EC requirements applicable.

The principles of the Declaration of Helsinki have been implemented through the patient informed consent process, EC approval, study training, clinical trial registration, preclinical testing, risk-benefit assessment and publication policy. The clinical trial filing will be completed prior to conduct of this study per the requirement of the Announcement of CFDA on Filing of the Medical Device Clinical Trial (2015, No. 87).

If the subject is below 18 years of age, he/she should be informed about the study to the extent compatible with the subject's understanding. If the subject could give consent to decisions about participation in research, the investigator must obtain that consent in addition to the consent of their legally authorized representative or guardian.

Regulatory Submission

Sponsor should be responsible for filing the study to Shanghai Municipal Food and Drug Administration after EC approval of the current version of the CIP and fully executed Clinical Trial Agreement.

Sponsor's Support

The sponsor shall avoid improper influence on, or inducement to, the subject, monitor, any investigator(s) or other parties participating in, or contributing to this study.

Sponsor representatives may provide support as required for the study, including technical support at investigational center. Sponsor representatives may provide technical support as required for the study under supervision of the PI, including:

- 1) Provide study training relevant and pertinent to the involvement of personnel conducting study activities and investigator responsibilities.
- 2) Technical support will be provided during study period.
- 3) Technical support will be under the supervision of a study investigator, but no data entry on the eCRF shall be performed by Medtronic personnel or their representatives at investigational centers.
- 4) Technical support to conduct device interrogations.

15.2. Investigator's Responsibilities

This study will be conducted at the investigational centers where all study-related activities will be performed and will be led by a PI. An investigator is an individual who actually conducts a clinical investigation (i.e., under whose immediate direction the test article is administered or dispensed to, or used involving, a subject) or, in the event of an investigation conducted by a team of individuals, is the responsible leader of that team.

The investigator's responsibilities include but are not limited to:

- Conduct of the investigation in accordance with the CIP, the regulations as outlined in CFDA that apply to this study and other applicable regulations, and any conditions of approval imposed by the reviewing EC
- Conduct of investigation in accordance to regulations from CFDA to meet responsibilities with respect to protect human subjects and ensuring the integrity of the data from clinical investigations. The regulations is also intended to clarify CFDA's expectations concerning the investigator's responsibility:
 - 1) to supervise a clinical study in which some study tasks are delegated to employees or colleagues of the investigator or other third parties, and
 - 2) to protect the rights, safety, and welfare of study subjects.
- Supervision of all testing of the device involving human subjects
- Ensuring that the requirements for obtaining informed consent are met in accordance with CFDA
- Allowing study devices to be used only with subjects under the investigator's supervision and to supply study devices only to persons authorized to receive it
- Ensuring that investigational center staff are adequately trained to perform their assigned duties
- Maintenance of accurate, complete, and current records relating to the investigator's part of an investigation, to include
 - all relevant correspondence with Medtronic and EC
 - records of receipt, use, or disposition of a device
 - records of each subject's case history and exposure to the device
 - the CIP, with documents showing the dates of and reasons for each deviation from the CIP

- Preparation and submission to Medtronic and, when required, the reviewing EC, the following complete, accurate, and timely reports:
 - any reportable AEs (see Section 11) occurring during an investigation
 - progress reports on the investigation as required by the EC
 - protocol deviation that may affect the subjects' rights and interests, safety, health or the scientificity of clinical trials, including deviation regarding requests and reports
 - any use of the device without obtaining informed consent
 - any further information requested by the EC about any aspect of the investigation
- Meeting with the monitor to discuss study progress and findings
- Ensuring that investigational center resources are adequate to fulfill the obligations of the study
- Ensuring completion of eCRF to include: entry and addressing discrepancies in a timely fashion and approving selected eCRFs. It is expected that data is entered into OC-RDC. Failure to keep up with entry of study data may result in study payment delay.

Only authorized study personnel, as listed on the Delegation of Authority Log, are permitted to consent subjects, receive, dispense, dispose of and return investigational products, conduct subject visits, insert devices and enter data on eCRFs. These tasks may be delegated by the investigator; however, the investigator is ultimately responsible to ensure Investigational Center staff are qualified and perform the tasks that have been delegated to them. In addition the investigator is responsible for the conduct of investigational center in the execution of the clinical trial.

The investigator's signature on the Investigator Statement and Signature Page confirms that the investigator is familiar with the CIP in its entirety and agrees to conduct this study in accordance with the provisions of the CIP and all applicable regulations. The investigator, prior to the initiation of any study related activity, will sign the Investigator Statement and Signature Page. If the sponsor discovers that an investigator is not complying with the Investigator Statement and Signature Page, CIP, or other regulatory requirements, the sponsor shall promptly secure compliance or discontinue that investigator's participation in the study.

16. Study Administration

